4.7. Temporary Suspension of Treatment

The Investigator has the right to suspend treatment with study drug for up to 14 continuous days. Subjects can miss up to 28 cumulative days of dosing without withdrawal of the subject from the study. Reasons for temporary suspension of treatment may include a medical reason unrelated to an AE (eg, a planned procedure) or important social or administrative events. The reason for the suspension of treatment is to be documented and source verified during monitoring visits.

When treatment is restarted, the subject should resume treatment with the next scheduled dose and continue until the scheduled EOT.

Subjects who develop hypercalcemia or hypercalciuria during the study are to have treatment with calcium and vitamin D temporarily suspended as described below. The Investigator should contact the sponsor for any planned suspension of treatment or if suspension of treatment is contemplated.

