### **4.3. Exposure to Study Drug**

#### **4.3.1. Extent of Exposure and Treatment Compliance**

Subjects were trained by study personnel on how to self-administer study drug with the abaloparatide-SC injection pen or the abaloparatide-sMTS patch. On the days of study site visits, study drug must be administered at the study site to accommodate pre-administration and post-administration procedures.

The overall duration of study drug exposure will be calculated using the data recorded on the eCRF as follows:

- Overall duration of study drug exposure (days) = (date of last dose – date of first dose) + 1.

If the date of last dose is missing, then the earlier of the following 2 dates will be used as the last dose date for analysis and summary purposes: the final visit/early termination visit date or the last drug dispense date + 30 days.

For the abaloparatide-SC group, the total number of doses delivered and study drug administration compliance will be calculated in two ways as follows:

- **Based on missed doses in subject diary:**
  - Number of doses delivered = Overall duration of study drug exposure – Total number of missed doses per subject diary
  - Percent compliance (%) to study drug administration =  $(\text{Number of doses delivered} / \text{Overall duration of study drug exposure}) \times 100\%$
- **Based on measurement of drug remaining in pen:**
  - Number of doses delivered =  $[(45.5 \text{ mm} \times \text{Number of used pens}) - \text{Sum of measurements of drug remaining in all used pens}] / 1.08 \text{ mm}$ . Here the 45.5mm is the initial measurement of unused study drug in an unused injection pen and 1.08mm is the distance the plunger travels for each 80 ug dose from the pen.

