The study drug exposure and percent compliance to study drug administration before 01 March 2020 and on or after 01 March 2020 will be summarized by treatment group for the Safety, mITT and PP populations. Similar summaries will not be provided by patch type (ultra-low bioburden, sterile) since the switch from ultra-low bioburden patch to sterile patch for subjects in abaloparatide- sMTS group did not occur until after 01 March 2020.

The number (%) of subjects with any missed dose or dose interruption as recorded on the Dose Interruption Log eCRF will be summarized by treatment group, along with the reason(s) for missed/interrupted dose(s) for the mITT, PP, and Safety populations. If a subject reported a start date for the missed/interrupted dose but no corresponding start date for the resumption of study drug, the occurrence of the missed dose/dose interruption will not be included in the summary. The total number of days with missed/interrupted dose for each subject will be calculated and summarized by descriptive statistics and in the following categories: 1-7 days, 8-14 days, 15-28 days, >28 days by treatment group.

Study drug exposure and study drug administration compliance data will be listed by treatment (including patch type for abaloparatide-sMTS group), study site, and subject number.

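### The dose-interruption summary omits every logged interruption without a resumption date, so that one table undercounts subjects, reasons and days

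*SAP*

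**What the plan says.** SAP 4.3.1 (Extent of Exposure and Treatment Compliance) will tabulate by treatment group "The number (%) of subjects with any missed dose or dose interruption as recorded on the Dose Interruption Log eCRF", "along with the reason(s) for missed/interrupted dose(s) for the mITT, PP, and Safety populations". It qualifies this at once: if a record has a start date but "no corresponding start date for the resumption of study drug, the occurrence of the missed dose/dose interruption will not be included in the summary". Each subject's total missed or interrupted days are then described "in the following categories: 1-7 days, 8-14 days, 15-28 days, >28 days by treatment group".

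The section gives no reason for the exclusion. It offers no substitute end date and no separate row for records that stay open.

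**The concern.** The table is presented as covering any missed dose or interruption, but the rule restricts it to those with a recorded restart. An interruption that runs into permanent stopping has no restart date, so it leaves the count, the reasons and the days. An interruption that did end is treated the same way if nobody entered the date.

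Safety and tolerability of the patch is a stated objective. Protocol 4.7 foresees suspension for hypercalcemia, for excessive skin irritation, and for reasons unrelated to an adverse event. If open records are more common in one arm, the table understates that arm more.

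**Working it through.** The plan states no figure to reproduce, so the check applies the rule to records and then looks for anything in the plan that restores what is lost.

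**Step 1: does another rule close an open record?** Appendix A, part 3 of the SAP is the catch-all for dates without a rule of their own. It handles partial dates only, so a wholly absent resumption date gets no value. The total-days sentence does not repeat the exclusion, but a record without an end date has no computable length. The days are therefore lost with the count and the reason.

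**Step 2: how does the SAP treat comparable gaps?**
- Missing last-dose date (SAP 4.3.1): use the earlier of the final or early-termination visit and the last dispensing date plus 30 days.
- Missing stop date for an adverse event of special interest (SAP 4.6.2): use the last study date.
- Missing resumption date (SAP 4.3.1): leave the occurrence out.

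In the first two cases a date is substituted. Only in the third is the record removed.

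**Step 3: apply the rule.** The subjects and dates below are assumptions. The closed days may come from several episodes. For comparison only, an open interruption is closed at withdrawal, with length = withdrawal day − start day + 1.

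| Subject | Closed days | Open interruption | SAP rule | Closed at withdrawal |
|---|---|---|---|---|
| A | 0 | day 200 to 235: 235 − 200 + 1 = 36 | 0, not counted | 36, >28 |
| B | 6 | same, 36 | 6, 1-7 | 6 + 36 = 42, >28 |
| C | 20 | day 200 to 212: 212 − 200 + 1 = 13 | 20, 15-28 | 20 + 13 = 33, >28 |
| D | 20 + 10 | none | 30, >28 | 30, >28 |

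A disappears from the table. B and C remain but fall into a lower category, and the reason for their last interruption is dropped. D shows that closed interruptions alone can fill the top category. A further type, an interruption that ended without its restart date being entered, is handled like the open record in A.

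**Step 4: effect on the percentage.** Assume all 237 randomized subjects per group are treated. Each subject whose only record is open lowers her arm's percentage by 100/237 = 0.42 points. If one arm has k more such subjects than the other, the reported difference shifts by about 0.42k points. The documents give no value for k.

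**Step 5: what is still reported elsewhere?**
- SAP 4.1: study drug discontinuations with primary reason.
- SAP 4.6.1: TEAEs leading to interruption and to withdrawal.
- SAP 4.6.2: the same counts for events of special interest.
- SAP 3.11: all available data in listings.

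Interruptions for non-AE reasons, such as the planned procedures and the social or administrative events named in Protocol 4.7, have no other table of occurrences and reasons. The nearest is the COVID-19 Impact Log summary in SAP 4.1, which has a category for missed or modified product but covers pandemic effects only.

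**The case against.** The strongest reply is that the rule separates two different things. Protocol 4.7 concerns temporary suspension, and a stop without restart can fairly be classed as a discontinuation. Counting it as both reports one event twice, and running the days to a discontinuation date or the EOT visit partly measures administrative delay. This has force for the day count. It does not justify the exclusion, because the SAP states no such purpose and the rule depends on a missing date rather than on treatment status. It therefore also removes interruptions that ended.

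The second reply is that skin-driven and calcium-driven stopping is visible elsewhere. That stands. Protocol 7.1.1 has all application-site skin reactions reported as AEs, and the TEAE tables carry no resumption-date condition. The arm comparison of tolerability does not rest on this summary.

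The third reply is that few records may be affected. The Dose Interruption Log instructions are not in the documents, and sites may record a permanent stop only as a discontinuation. That also stands, although the SAP sentence shows that its authors expected records with no restart date.

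A reader might also infer two stronger points that the documents do not support.
- **That the lost days vanish from compliance, giving 100%.** SAP 4.3.1 subtracts the missed doses in the diary from the exposure duration, and does not limit them to doses before the last one taken. Assume 200 days of exposure and 14 suspended days after the last dose. If these are entered as missed, compliance is (200 − 14)/200 = 93%; if they are not entered, it is 100%. The documents do not settle which.
- **That the >28-day category conflicts with Protocol 4.7.** The protocol says "Subjects can miss up to 28 cumulative days of dosing without withdrawal of the subject from the study" but not what follows after day 28. Protocol 4.3.1 lists noncompliance and protocol deviations only as reasons for which the Investigator may consider stopping. Subject D shows that the category can be filled.

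**Conclusion.** The point holds for this one descriptive table. Followed as written, the rule misreports the quantity that the table says it shows: subjects, reasons and days can all be too low. The number affected is unknown and depends on how sites complete the log.

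The direction of any distortion between arms is conditional. The arm with more open records is understated more, and the documents do not say which arm that would be. A reader might infer that the trial's tolerability comparison is biased towards the worse-tolerated arm. The documents do not support that, because the TEAE, special-interest and disposition tables remain.

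No inferential result changes. The primary MMRM, the margin and the sample size do not use this summary. The drug-administration criteria for per-protocol exclusion in SAP Appendix B are exposure under 90 days and compliance under 80%.

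**What to change.** Delete the exclusion sentence in SAP 4.3.1 and replace it with text to this effect: *Every occurrence on the Dose Interruption Log is included in the subject count and the reason rows, overall and split into resumed and not resumed or resumption date missing. Total days and their categories are based on resumed interruptions and labelled accordingly.*

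Optionally, add a supplementary day count for open interruptions with a cut-off fixed in advance, for example the recorded treatment discontinuation date. The last-dose date should not be the cut-off, because it would give zero days. This count is secondary, because part of the interval may be administrative delay.

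The cost is one SAP sentence and minor programming. Some subjects will also appear in the discontinuation table, and the not-resumed flag makes that overlap plain. If the analysis plan can no longer be amended, SAP Section 1 allows the table to be added as an unplanned analysis identified in Section 9.8 of the clinical study report.

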#### **4.3.1.1. Residual Drug Amount of Abaloparatide-sMTS**

For the abaloparatide-sMTS group, residual drug amount from patches and skin swabs obtained at study site visits on Days 1 and 14 and Months 1, 3, 6, and 9 will be provided by Kindeva (previously 3M). The residual drug amount from patches and skin swabs will be used to determine the patch released dose, defined as:

Patch Released Dose = (initial patch content) – (patch residual drug amount) – (swab residual drug amount).

Initial patch content will be measured by Kindeva at the time of lot release and will be based on the average of 6 samples per lot. If the swab residual drug amount is missing, the patch released dose will be calculated based on initial patch content and patch residual drug amount. If the patch residual drug amount is missing, the patch released dose will be considered as missing.

Descriptive statistics for the safety population will be used to summarize the patch released dose, the percentage of released dose to nominal dose, the percentage of released dose to initial patch content, the residual drug amount from patch, the residual drug amount from swab, and the residual drug amount from patch and swab, by visit for Days 1 and 14, Months 1, 3, 6, and 9, and overall for the abaloparatide-sMTS group.

The summaries will also be presented by patch type (ultra-low bioburden, sterile).

#### **4.3.2. Abaloparatide-sMTS Patch Adhesion Scores**

Patch adhesion will be assessed daily by subjects randomized to the abaloparatide-sMTS treatment group using the following scoring system:

- 0 =  $\geq 90\%$  adhered (essentially no lift off the skin)
- 1 =  $\geq 75\%$  to  $< 90\%$  adhered (some edges only lifting off the skin)
- 2 =  $\geq 50\%$  to  $< 75\%$  adhered (less than half of the patch lifting off the skin)
- 3 =  $> 0\%$  to  $< 50\%$  adhered but not detached (more than half of the patch lifting off skin without falling off)
- 4 = 0% adhered – patch detached (patch completely off the skin)

A summary table using descriptive statistics will be provided combining all patch adhesion scores collected in the study. Frequency counts (and percentages) of all patch adhesion scores will be presented. The summaries will also be presented by patch type (ultra-low bioburden, sterile).

The mean of the patch adhesion scores collected from Day 1 to Month 12/EOT will be calculated for each subject and summarized using descriptive statistics. Each subject's best adhesion score and worst adhesion score will also be summarized. In addition, frequency counts (and percentages) for each subject's best adhesion score and for each subject's worst adhesion score from Day 1 to Month 12/EOT will be provided. For subjects treated with both patch types (ultra-low bioburden, sterile), the mean patch adhesion scores will also be calculated for each patch type for each subject for the respective period of treatment of the patch type. Each subject's best adhesion score and worst adhesion score by patch type will also be summarized for the respective period of treatment of the patch type. Frequency counts (and percentages) for each subject's best adhesion score and for each subject's worst adhesion score by patch type will be presented for the respective period of treatment of the patch type.

The percentage of patches that are  $\geq 75\%$  adhered (adhesion score  $\leq 1$ ) will be summarized by patch type and overall for abaloparatide-sMTS treatment group. Statistical assessment of patch adhesion will be evaluated via the following hypothesis test:

- $H_0: p \leq 80\%$  versus  $H_1: p > 80\%$
- $H_0$  is rejected if the 95% lower confidence limit for  $p$  is greater than 80%

where  $p$  is the estimated percentage of patches that are  $\geq 75\%$  adhered. Two-sided 95% CIs for  $p$  will be provided for each patch type and overall using a model-based method as primary analysis and using Wilson's Score method as sensitivity analysis. Considering that for each subject, the patch adhesion score is collected daily using the subject diary during the treatment period, the model-based method will use a GEE (Generalized Estimating Equation) model assuming binomial distribution and including treatment group as fixed categorical effect with an unstructured correlation matrix to model the within-subject errors. For patch type comparison, the model will include patch type as fixed categorical effect. The p-value will be reported for patch type difference (ultra-low bioburden vs sterile).

All analyses described in this section will be presented for the Safety, mITT and PP populations. The analysis will not be provided for the ITT population since untreated subjects in the ITT population will not have exposure data.

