### **1.2. Study Design**

#### **1.2.1. Synopsis of Study Design**

This is a randomized, open-label, non-inferiority, multicenter study of abaloparatide-sMTS compared with abaloparatide-SC for the treatment of postmenopausal women with osteoporosis.

[figure not shown]
The study will consist of a Screening Period (up to 2 months), a Pretreatment Period (1 week), and a Treatment Period (12 months) with a final visit 1 month after the last dose of study drug (Follow-Up/End of Study [EOS] visit). 1 month is defined as 30 days in this study. Thus, subjects will participate in the study for up to 16 months.

Eligible subjects will be randomized in a 1:1 treatment ratio to either abaloparatide-sMTS or abaloparatide-SC using a permuted block randomization scheme. During the Treatment Period, subjects will self-administer study drug once a day for 12 months and visit the study site on Days 1 and 14 and Months 1, 2, 3, 4, 5, 6, 7, 8, 9, 10, 11, 12 and Month 13 for the follow-up visit.

All subjects will be provided calcium and Vitamin D to ensure that their daily intake is 1200 mg/day and 800 IU/day, respectively, or a dose determined by the investigator and agreed by the Sponsor Medical Monitor according to the subject's need.

The study design is presented in [Figure 1](#).

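### The Wilson sensitivity interval for patch adhesion ignores repeated patches within subjects, so it cannot check the robustness of the GEE interval

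*SAP*

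**What the plan says.** SAP 4.3.2 sets a formal test on the device. The null hypothesis, that p is at most 80%, "is rejected if the 95% lower confidence limit for" p is above 80%. The unit is the patch, not the subject: p "is the estimated percentage of patches that are" at least 75% adhered.

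Two-sided 95% intervals are planned overall and for each patch type, "using a model-based method as primary analysis and using Wilson's Score method as sensitivity analysis". The reason given for the model is repetition over days, and it follows directly on the naming of Wilson's "Score method as sensitivity analysis. Considering that for each subject, the patch adhesion score is collected daily using the subject diary". The GEE is specified "with an unstructured correlation matrix to model the within-subject errors". For Wilson, the section states no design effect, effective sample size or other allowance for repeated scores.

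The number of repeats follows from the design. "Patch adhesion will be assessed daily by subjects randomized to the abaloparatide-sMTS treatment group", and under SAP 1.2.1 "subjects will self-administer study drug once a day for 12 months", where "1 month is defined as 30 days in this study".

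**The concern.** A sensitivity analysis should vary an assumption that might be wrong and show whether the conclusion survives. Here the alternative drops the within-subject correlation, which the SAP has just recognised as a feature of the data. Wilson's formula needs independent observations. Applied to a percentage of patches, it counts one woman's several hundred daily scores as if each came from a different woman.

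The SAP does not say in words that patches are pooled as independent. That follows from the definition of p together with an unadjusted Wilson interval.

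At stake is the reading of the 80% test. If the two intervals agree, the agreement says little, because plain Wilson understates the uncertainty whenever correlation is positive. If they disagree, a reader has no stated basis for setting Wilson aside. The same applies to each patch type.

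**Working it through.** **Inputs from the documents.** The SAP gives no power, expected adhesion rate or ICC for this test, so it has no adhesion figure to reproduce. The number of clusters comes from SAP 3.1: 426 / 0.90 = 473.3, taken to 474, or 237 per group. Patches per subject: 12 × 30 = 360 at most. The test uses the lower limit of a two-sided 95% interval, so the nominal one-sided error is 2.5%.

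**Assumed.** The ICC (range shown), constant correlation between any two days, and the same number of patches m for every subject.

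**Plain Wilson width.** 237 × 360 = 85,320 patches. At 80% the half-width is about 1.96 × √(0.8 × 0.2 / 85,320) = 0.0027, or 0.27 percentage points.

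**Effect of clustering.** Design effect D = 1 + (m − 1) × ICC. The interval is too narrow by a factor of √D. At a true p of exactly 80%, the Wilson version rejects with probability 1 − Φ(1.96 / √D). For ICC 0.02 and m = 360: D = 1 + 359 × 0.02 = 8.18, √D = 2.86, and 1 − Φ(0.685) = 25%. The coverage column comes from a beta-binomial simulation of the plain Wilson interval with 237 subjects; its rejection rates matched the formula to within about 1 percentage point.

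| Assumed ICC | D (m = 360) | √D (m = 360) | Rejects at true 80% | Simulated coverage | √D (m = 180) |
|---|---|---|---|---|---|
| 0 | 1.0 | 1.0 | 2.5% | 95% | 1.0 |
| 0.01 | 4.6 | 2.1 | 18% | 64% | 1.7 |
| 0.02 | 8.2 | 2.9 | 25% | 51% | 2.1 |
| 0.05 | 19.0 | 4.4 | 33% | 35% | 3.2 |
| 0.10 | 36.9 | 6.1 | 37% | 26% | 4.3 |
| 0.30 | 108.7 | 10.4 | 43% | 15% | 7.4 |

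A factor of 10 needs ICC 0.276, since 1 + 359 × 0.276 = 100.1. The column for m = 180 stands for a subject who spends about half the treatment period on one patch type.

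**If correlation decays over time.** Under an assumed first-order autoregressive pattern with adjacent-day correlation 0.3, D is about (1 + 0.3) / (1 − 0.3) = 1.86. Then √D = 1.4, and rejection at a true 80% is 1 − Φ(1.96 / 1.36) = 7.5%.

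**Does the conclusion change?** The approximate lower limit is p̂ − 1.96 × √(p̂(1 − p̂) × D / 85,320).

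| Observed | Plain | ICC 0.02 | ICC 0.10 | ICC 0.30 |
|---|---|---|---|---|
| 82% | 81.7% | 81.3% | 80.4% | 79.3% |
| 90% | 89.8% | 89.4% | 88.8% | 87.9% |

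At an observed 82% and ICC 0.30, plain Wilson rejects and a clustered interval does not. At an observed 90%, every limit stays above 80%. The excess rejection also falls off quickly below 80%: at a true 78% with m = 360 it is under 1% at ICC 0.10 and about 6% at ICC 0.30.

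**The case against.** The strongest reply is that Wilson is only the sensitivity analysis. The primary interval comes from a GEE that models the correlation, so a reader who infers that the trial's adhesion test itself rejects too often goes further than the SAP supports. That reply stands: the rejection rates above belong to the Wilson version alone. One might answer that the GEE could fail, leaving only Wilson. An unstructured matrix over 360 days has 360 × 359 / 2 = 64,620 correlations for 237 subjects, and no fallback is named. This is a fair question about the GEE, but the documents do not show that it will fail, and it is a separate matter.

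Three more limits stand. First, no multiplier can be stated as fact, because the ICC is unknown and the factor shrinks with fewer patches or decaying correlation. Second, it is tempting to say that so narrow an interval will confirm the primary result whatever it is. It will not: in the 82% example it would visibly contradict a clustered interval. Third, one might argue that women whose patches do not stick leave early and so count least. The documents do not support this. Protocol 4.3.1 does not list poor adhesion among the reasons for withdrawal, and weighting by patch follows from the SAP's own definition of p.

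The consequences are also contained. Adhesion is not in the endpoint lists of Protocol 2.2 or SAP 1.2.5, the test sits in the exposure section, and the BMD non-inferiority decision does not use it. SAP 4.3.2 already plans per-subject mean, best and worst scores.

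None of this makes plain Wilson a valid check. The direction of its error is certain for any positive within-subject correlation.

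**Conclusion.** The point holds for the sensitivity interval. Plain Wilson on patch counts is too narrow under any positive within-subject correlation and cannot show that the GEE interval is robust. With 237 subjects, 360 patches each and constant correlation, the factor is about 2 at ICC 0.01, 3 at 0.02 and 10 at 0.28 to 0.30. With about 180 patches per patch type it is 2.1 to 7.4 for ICC 0.02 to 0.30. These ICCs are assumptions, and decaying correlation gives smaller factors. Rejection of about 18% to 43% instead of 2.5% applies to the Wilson version at a true rate of exactly 80%. The choice of interval can therefore alter the conclusion only when adhesion is close to 80%. The primary GEE analysis and the BMD endpoint are outside this finding.

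**What to change.** Replace the plain Wilson interval in SAP 4.3.2, overall and for each patch type, with one that keeps p as defined and respects clustering. Either option works:

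- a bootstrap that resamples subjects, keeps all of each subject's patches, and recomputes the pooled patch percentage; or
- Wilson's method with effective n = number of patches / estimated design effect.

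Compare that lower limit with 80%. A t interval on per-subject percentages would also respect clustering, but it weights subjects equally and so estimates a different quantity from p. If plain Wilson is kept, label it descriptive and state that it plays no part in the 80% decision rule.

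The cost is a change of SAP wording, a short program, and a wider reported interval.

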## **1. BACKGROUND**

This statistical analysis plan (SAP) enhances the statistical considerations specified in the protocol for non-pharmacokinetic (PK) data for Study BA058-05-021. If considerations are substantially different, they will be identified. Any post-hoc or unplanned analyses, or any significant changes from the planned analysis in this SAP will be clearly identified in Section 9.8 of the clinical study report (CSR). The final SAP will be included as an appendix to the final CSR.

The method for analyzing the PK data will be described in the Pharmacometric Analysis Plan (PAP) as a separate document.

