### **3.3. Computing Environment**

All descriptive and statistical analyses will be performed using SAS statistical software Version 9.4 or later version. Medical history and AEs will be coded using the Medical Dictionary for Regulatory Activities (MedDRA), Version 24.0. Concomitant medications will be coded using the World Health Organization Drug Dictionary (WHO-DD) March 2018 B3.

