Two different patches will be dispensed to subjects in the abaloparatide-sMTS group. The ultra-low bioburden patches will be dispensed from Day 1 to all subjects. Sterile patches (the patches intended for commercial use) will be dispensed to subjects after confirmation that the sterile product is bioequivalent to the ultra-low bioburden product (Study 058-05-023). For the abaloparatide-sMTS group, the duration of study drug exposure, duration category in months, number of doses delivered and percent compliance with study drug administration using two calculations of percent compliance will also be summarized by patch type (ultra-low bioburden, sterile) for the Safety, mITT and PP populations.

If a subject is shown to be  $<80\%$  compliant with study drug administration using both calculations of study drug administration compliance for abaloparatide-sMTS group, or is  $<80\%$  compliant with study drug administration using both calculations of study drug administration compliance for the abaloparatide-SC group, this subject will be considered as having a critical protocol deviation and thus excluded from the PP Population.

Subjects' drug exposure and compliance will be carefully reviewed against the onset of the COVID-19 pandemic. Each subject's study drug exposure and compliance prior to 01 March 2020 and on or after 01 March 2020 will be calculated based on information collected from the subject diary:

- For subjects with last dose date prior to 01 March 2020 and subjects with first dose date on or after 01 March 2020, their duration of study drug exposure (days), number of doses delivered, and percent compliance to study drug administration relative to 01 March 2020 will be calculated as above based on the missed doses in subject diary
- For subjects who started taking the study drug prior to 01 March 2020 and continued on or after 01 March 2020, their duration of study drug exposure and compliance before 01 March 2020 and on or after 01 March 2020 will be calculated as follow:
  - Durations of study drug exposure relative to 01 March 2020:
    - Duration before 01 March 2020 = 29 February 2020 – date of first dose + 1
    - Duration on or after 01 March 2020 = Overall duration of study drug exposure – duration before 01 March 2020; where overall duration of study drug exposure = last dose date – first dose date + 1

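### The primary patch-adhesion GEE asks for 64,620 correlations from about 237 patients, failed in most or all simulated runs, and has no fallback; the patch-type p-value is also confounded with time on treatment

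*SAP*

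**What the plan says.** SAP section 4.3.2 sets a formal rule for adhesion: reject H0: p ≤ 80% if the 95% lower confidence limit for p exceeds 80%, where p is the percentage of patches at least 75% adhered. The interval is obtained "using a model-based method as primary analysis and using Wilson's Score method as sensitivity analysis". The model-based method is a binomial GEE "including treatment group as fixed categorical effect with an unstructured correlation matrix to model the within-subject errors". The stated reason for it is that "the patch adhesion score is collected daily using the subject diary during the treatment period". No reduction of the daily scores to visits or months is given for this model, and no alternative structure is named if the fit fails.

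The same GEE, with patch type as the fixed effect, is the only source of the p-value for ultra-low bioburden against sterile patches. SAP section 4.3.1 shows how patch type arises: "The ultra-low bioburden patches will be dispensed from Day 1 to all subjects", with sterile patches dispensed once bioequivalence is confirmed. It places "the switch from ultra-low bioburden patch to sterile patch" after 01 March 2020.

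Two other provisions bear on this. Section 3.3 states: "All descriptive and statistical analyses will be performed using SAS statistical software Version 9.4 or later version". Section 1 states: "any significant changes from the planned analysis in this SAP will be clearly identified in Section 9.8" of the clinical study report.

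**The concern.** There are more days per patient than patients. An unstructured working correlation then has far more parameters than the data can support, and the estimated matrix cannot be expected to be usable as a weight matrix. If the prespecified primary fit does not converge, the analyst must choose a replacement after seeing the data. Section 1 requires that change to be disclosed but does not say what the replacement is. The only prespecified interval left would be Wilson's, which treats every patch as independent and gives no patch-type p-value.

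A second problem does not depend on the correlation structure. Every sMTS patient starts on one patch type and any switch comes later. A trend in adhesion over time on treatment would therefore appear as a patch-type difference, yet the SAP does not label this p-value exploratory.

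**Working it through.** **Inputs from the documents.** Planned sMTS arm: 237 (SAP 3.1). Scoring: daily (SAP 4.3.2; protocol 6.6.5). Treatment: 12 months of 30 days (protocol 6.2; SAP 1.2.1), so up to 12 × 30 = 360 scores per patient.

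**The plan's own figure.** The adhesion section states no sample size. The trial size that supplies the patients reproduces: a margin of 2.0, SD 6.35, one-sided 0.025 and 90% power give 212 per arm, or 424 (stated 426). Power with 213 per arm is 90.2%, and 426 / 0.90 rounds up to 474, or 237 per arm.

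**Parameter count.** 360 × 359 / 2 = 64,620 correlations, from 237 × 360 = 85,320 scores at most. Only the sMTS arm is scored, so the treatment-group effect has one level and is just the intercept.

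**Condition of the matrix.** With complete records the moment matrix scaled day by day has rank at most 237 out of 360, so it is singular. With a unit diagonal and one common dispersion, the simulated matrix was indefinite: 75 to 84 negative eigenvalues with complete records (20 datasets), and 116 to 136 with 5% missed days and 20% dropout (26 datasets).

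**Convergence, first set** (237 patients, 360 days, assumed p = 90%, intraclass correlation [ICC] 0.10 unless stated, at most 50 iterations):

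| Records | Model | Result |
|---|---|---|
| 5% missed days, 20% dropout | overall | 26 of 26 diverged |
| same | patch type | 26 of 26 diverged |
| ICC 0.01; ICC 0.30; or 2% missed days with 10% dropout (3 runs each) | overall | 9 of 9 diverged |
| complete | overall | 8 diverged, 5 did not converge, 7 converged |

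The 7 converged estimates were 0.0 to 2.7 points from the observed percentage (worst: 93.6% against 90.9%).

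**Convergence, second set** (separate code; random-intercept data with p = 86.3%, or autoregressive data with p = 90%; 1% or 5% missed days plus 15% dropout). Both models diverged in all 80 incomplete-record datasets (40 + 20 + 20). With complete random-intercept records, 42 of 100 overall fits converged, with estimates from 67.5% to 99.3% and 52% coverage; 3 of 100 patch-type fits converged. Independence and exchangeable structures converged every time on the same data.

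**What Wilson would do instead.** The design effect is 1 + 359 × ICC, and the width ratio is its square root. The smallest observed p that passes is 80% + 1.96 × √(0.8 × 0.2 / n). With n = 85,320 Wilson passes at 80.27%. Dividing n by the design effect gives:

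| ICC | Design effect | Width ratio | Smallest passing p |
|---|---|---|---|
| 0.001 | 1.36 | 1.2 | 80.31% |
| 0.01 | 4.59 | 2.1 | 80.58% |
| 0.05 | 18.95 | 4.4 | 81.17% |
| 0.10 | 36.9 | 6.1 | 81.63% |
| 0.30 | 108.7 | 10.4 | 82.80% |

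The 80% decision changes only if observed adhesion falls between 80.27% and the value in the last column.

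**Patch-type confounding.** Assumptions: no true patch effect, p = 90%, linear drift over 360 days, 60% of patients switching between days 90 and 300, 600 simulations per cell, correctly clustered test. The spurious patch difference averages about 0.3 / 0.7 / 1.4 points for a drift of 1 / 2 / 4 points. Rejection at the nominal 5%:

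| ICC | 1 point | 2 points | 4 points |
|---|---|---|---|
| 0.01 | 15.2% | 46.3% | 97.2% |
| 0.10 | 9.8% | 13.0% | 37.2% |
| 0.30 | 6.8% | 8.5% | 17.7% |

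At ICC 0.10, for drifts of 2 / 4 points, 30% switching gives 6.8 / 15.8% and 90% switching gives 22.0 / 76.5% (400 simulations).

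**The case against.** **The daily index is inferred.** The SAP never names the within-subject index, and section 4.6.4.2 reduces another daily diary measure to monthly periods and to site-visit days. With 14 site-visit scores (91 correlations) all 100 fits converged, although coverage of p was 89%. With monthly aggregates, 200 / 170 / 119 of 200 fits converged at ICC 0.01 / 0.10 / 0.30. So another reading softens the problem without clearing it. No such reduction is stated for adhesion, and daily collection is the reason given for the model.

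**Software and assumptions.** The simulations are in Python, not SAS, and the adhesion, ICC, missingness, drift and switching values are assumed because the documents give none. Failure shares could differ in SAS. The ratio of 64,620 correlations to 237 patients does not depend on software. The 237 is the planned arm size (SAP 1.2.2 says approximately 474 in total), and a few more patients change nothing. Some confounding figures are close to noise: 6.8% at ICC 0.30 with a 1-point drift compares with 5.8% with no drift.

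**Confounding can be reduced.** If patients switch on different study days, patch type is not fully aliased with time. In a rerun of the linear-drift scenario (300 runs per cell), unadjusted rejection for drifts of 2 / 4 points was 43 / 95%, 9 / 26% and 9 / 10% at ICC 0.01, 0.10 and 0.30. With study day as a covariate it was 5 / 6%, 3 / 5% and 6 / 6%. This stands as a useful addition. It would not cover non-linear drift or calendar effects, so the exploratory label is still needed.

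**Consequence.** Adhesion is not a listed endpoint, frequency counts by patch type need no model, and the 80% decision is at risk only in a narrow band. That stands and limits the point to minor.

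**Conclusion.** The concern holds and is minor. On the natural daily reading, the prespecified primary method cannot be relied on to give an answer: it diverged in every simulated dataset with incomplete diaries, failed in most with complete ones, and was unreliable where it converged. Incomplete diaries are the realistic case, since the SAP itself counts missed doses and does not replace withdrawals. The failure rates rest on the assumed data models and on code other than SAS; the parameter count does not.

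The patch-type p-value has a separate weakness, because patch type follows time on treatment and was not randomized. How large the resulting bias is depends entirely on the assumed drift and switching pattern.

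The effect is confined to the adhesion test and the patch-type comparison, which SAP section 5 lists as added to the protocol analyses.

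**What to change.** In SAP section 4.3.2:

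- Replace the unstructured matrix with an independence working correlation and empirical (sandwich) standard errors clustered on patient. Use an intercept-only model for the overall p, and patch type as the fixed effect for the comparison.
- Label the Wilson interval descriptive, because it ignores clustering within patient.
- State that the patch-type p-value is exploratory, because patch type is not randomized and is confounded with time on treatment. A study-day covariate could be added to that model.

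The replacement was checked in 4,000 simulations per ICC (true p = 80%, 5% missed days, 20% dropout, 60% switching, no time trend):

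| ICC | Coverage of p, replacement | Patch-type type I error | Coverage of p, Wilson |
|---|---|---|---|
| 0.01 | 95.0% | 5.1% | 65.5% |
| 0.05 | 95.3% | 5.0% | 35.8% |
| 0.10 | 94.6% | 5.4% | 25.7% |
| 0.30 | 93.9% | 5.8% | 15.2% |

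The cost is SAP wording only, with no new data. The interval will be wider than Wilson's. The new standard errors do not remove the patch-type confounding, which is why the label is needed as well.
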